4.2.3.2 Safety Endpoints

Adverse events (AEs) will be documented on a validated vaccination report card (VRC). The VRC was developed to be administered electronically via a hand-held device. All AEs will be assessed for intensity.

1. Trial subjects will be observed for 30 minutes postvaccination for any immediate AEs.
2. Solicited injection-site AEs (redness, swelling, hard lump, and pain/tenderness) and solicited systemic AEs (irritability, drowsiness, hives/welts, and appetite lost) will be collected Day 1 to Day 14 after each vaccination.
3. Any other unsolicited systemic or injection-site AEs will be collected Day 1 to Day 14 after each vaccination.
4. Serious AEs will be collected from the time the consent form is signed through 30 days PD4 and/or completion of the subject's participation in the trial. Refer to Section 7.2.2.1 for complete detail on serious AE data collection.
5. Body temperature will be measured during Day 1 to Day 7 after each vaccination. If fever is suspected, temperature will also be measured during Day 8 to Day 14 postvaccination.

The 14-day safety follow-up period for AEs occurring following receipt of each dose of the trial vaccine is consistent with other clinical trials evaluating the safety of licensed pneumococcal conjugate vaccines in healthy infants.

Safety Monitoring

Safety and tolerability profiles will be carefully monitored throughout the trial by the SPONSOR in accordance with standard procedures and also by an external Data Monitoring Committee (eDMC). Please see Section 7.3.2 Data Monitoring Committee for details regarding the composition, roles and responsibilities of the eDMC.

In order to evaluate the safety profile of V114 in infants, VRC-prompted injection-site adverse events (redness, swelling, hard lump [rated by size] and pain/tenderness) and VRC-prompted systemic adverse events (irritability, drowsiness, appetite lost, hives/ welts) will be recorded for 14 days. If a hard lump at the injection site is present for 72 hours, the subject's parent/legal guardian should immediately contact the site to schedule an appointment with the trial site for an evaluation within 48 hours, where the trial doctor will diagnose the injection-site reaction (e.g., induration or nodule). If hives/welts (urticaria) occur, the subject's parent/legal guardian should immediately contact the site to schedule an appointment with the trial site for an evaluation within 48 hours, where the trial doctor will determine whether the hives/welts represent an urticarial-like eruption. Unsolicited systemic or injection-site adverse events or serious adverse events will be collected from Day 1 through Day 14 after each vaccination. Serious adverse events (regardless of the investigator's assessment of causality) from the time the consent form is signed through completion of the subject's participation in the trial at 30 days after the last dose of trial vaccine will be collected (see Section 7.2 for details). Any immediate adverse events occurring in the 30 minutes postvaccination observation period will be recorded. Information about any medications, including any analgesic/antipyretic use on the day of

vaccination that the subject receives, should be documented throughout the trial on the VRC for the 14-day safety follow-up period following each vaccination.

4.2.3.3 Future Biomedical Research

cc1 [REDACTED]

[REDACTED]

[REDACTED]

[REDACTED]

4.3 Benefit/Risk

Subjects in clinical trials generally cannot expect to receive direct benefit from vaccination during participation, as clinical trials are designed to provide information about the safety and efficacy of an investigational medicine.

A subset of subjects will receive Prevnar 13™ which is the standard of care and is serving as the active comparator in this trial. V114 is aimed at providing comparable immune responses to Prevnar 13™ for the shared serotypes while providing additional coverage for the 2 serotypes (22F and 33F) unique to V114. It is unknown if the investigational V114 will have the same benefit as Prevnar 13™. As a possible rescue medication in this trial, subjects who fail to achieve adequate immune responses to serotype 19A (individually) or to 4 or more other serotypes in common between Prevnar 13™ and V114 following the third dose of trial vaccine will be offered an additional dose of licensed pneumococcal conjugate vaccine as soon as possible after serology results are available. (See Section 5.6 Rescue Medications & Supportive Care for additional details).

Additional details regarding specific benefits and risks for subjects participating in this clinical trial may be found in the accompanying Investigators Brochure (IB) and Informed Consent documents.

5.0 METHODOLOGY

5.1 Entry Criteria

5.1.1 Diagnosis/Condition for Entry into the Trial

Healthy male and female infants approximately 2 months of age (between 42 and 90 days old) (inclusive) will be enrolled in this trial.

5.1.2 Subject Inclusion Criteria

In order to be eligible for participation in this trial, the subject must:

1. Be healthy (based on medical history and physical examination) male or female infant approximately 2 months of age (42 days to 90 days), inclusive.
2. Have a parent/legal guardian who understands the trial procedures, alternate treatments available, and risks involved with the trial.
3. Have a parent/legal guardian who is able to read, understand, and complete the VRC and voluntarily agree to participate by giving written informed consent.
4. A parent/legal guardian also acknowledges that they:
 - a. will attend all scheduled visits
 - b. comply with the trial procedures, and
 - c. have access to a telephone.

5.1.3 Subject Exclusion Criteria

The subject must be excluded from participating in the trial if the subject:

If the subject meets criteria marked with an asterisk (*), the Day 1 Visit may be rescheduled for a time when these criteria are not met.

1. Had prior administration of any pneumococcal vaccine.
2. Has a known hypersensitivity to any component of the pneumococcal conjugate vaccine, or any diphtheria toxoid-containing vaccine.
3. *Had a recent febrile illness (rectal temperature $\geq 38.1^{\circ}\text{C}$ [$\geq 100.5^{\circ}\text{F}$] or axillary temperature $\geq 37.8^{\circ}\text{C}$ [$\geq 100.0^{\circ}\text{F}$]) occurring within 72 hours prior to receipt of trial vaccine.
4. Has a known or suspected impairment of immunological function.
5. Has a history of congenital or acquired immunodeficiency (e.g. splenomegaly).
6. Has or his/her mother has a documented human immunodeficiency virus (HIV) infection.
7. Has or his/her mother has a documented hepatitis B surface antigen – positive test.
8. Has known or history of functional or anatomic asplenia.
9. Has a history of failure to thrive.

10. Has known or history of a coagulation disorder contraindicating intramuscular vaccination.
11. Has a history of autoimmune disease including systemic lupus erythematosus, anti-phospholipid syndrome, Behcet's disease, autoimmune thyroid disease, polymyositis and dermatomyositis, scleroderma, type 1 diabetes mellitus, and other autoimmune disorders.
12. Has a known neurologic or cognitive behavioral disorder, including encephalitis/myelitis, acute disseminating encephalomyelitis, pervasive development disorder, and related disorders.
13. *Meets one or more of the following systemic corticosteroid exclusion criteria:
 - Has received systemic corticosteroids (equivalent of ≥ 2 mg/kg total daily dose of prednisone or ≥ 20 mg/d for persons weighing > 10 kg) for ≥ 14 consecutive days and has not completed this course of treatment at least 30 days prior to trial randomization.
 - Has received systemic corticosteroids within 14 days prior to the first dose of vaccine at randomization.
 - Is expected to require systemic corticosteroids within 30 days after each vaccination during conduct of the trial..
14. *Has received other licensed non-live vaccines within the 14 days before receipt of first dose of trial vaccine.
15. *Has received a licensed live virus vaccine within the 30 days prior to receipt of first dose of trial vaccine.
16. Had prior receipt of a blood transfusion or blood products, including immunoglobulins.
17. Has participated in another clinical trial of an investigational product before the beginning or anytime during the duration of the current clinical trial. Subjects enrolled in observational studies may be included; these will be reviewed on a case-by-case basis for approval by the SPONSOR.
18. Has a history of invasive pneumococcal disease (positive blood culture, positive cerebrospinal fluid culture, or other sterile site) or known history of other culture positive pneumococcal disease.
19. Cannot be adequately followed for safety according to the protocol plan.
20. Has a parent/legal guardian who is unlikely to adhere to trial procedures, keep appointments, or is planning to relocate during the trial.
21. Has any other reason that in the opinion of the investigator may interfere with the evaluation required by the trial.
22. Is or has an immediate family member (e.g., spouse, parent/legal guardian, sibling or child) who is investigational site or sponsor staff directly involved with this trial.

5.2 Trial Vaccination(s)

The vaccines to be used in this trial are outlined below in [Table 1](#).

Table 1 Trial Vaccinations

Trial Vaccines	Dose/Potency	Dose Frequency	Route of Administration	Regimen/Vaccination Period	Use
V114-1 (Lot 1)	0.5 mL	1	Intramuscular injection ¹	Each subject will receive 4 doses of the trial vaccine given at approximately 2, 4, 6, and 12 to 15 months of age.	Investigational
V114-2 (Lot 2)	0.5 mL	1	Intramuscular injection ¹	Each subject will receive 4 doses of the trial vaccine given at approximately 2, 4, 6, and 12 to 15 months of age.	Investigational
Prevnar 13™	0.5 mL	1	Intramuscular injection ¹	Each subject will receive 4 doses of the trial vaccine given at approximately 2, 4, 6, and 12 to 15 months of age.	Active Comparator

¹Each trial vaccine is to be injected into the deltoid muscle of the upper arm.

Trial vaccination (first dose of trial vaccine) will be given on the day of treatment allocation/randomization or as close as possible to the date on which the subject is allocated/assigned.

The investigator shall take responsibility for and shall take all steps to maintain appropriate records and ensure appropriate supply, storage, handling, distribution and usage of trial treatments in accordance with the protocol and any applicable laws and regulations.

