2.0 TRIAL DESIGN

2.1 Trial Design

This is a multicenter, randomized, double-blind trial to evaluate the safety, tolerability, and immunogenicity of 2 different lots of V114 in healthy infants to be conducted in conformance with Good Clinical Practices (GCPs). Prevnar 13™ (pneumococcal 13-valent conjugate vaccine [diphtheria CRM₁₉₇ protein], Wyeth Pharmaceuticals, Inc., Philadelphia, Pa) will serve as the active control. This trial will enroll approximately 1,050 healthy infants 6 to 12 weeks (≥ 42 to ≤ 90 days) of age. Subjects will be randomly assigned to receive V114 Lot 1 (n=350), V114 Lot 2 (n=350) or Prevnar 13™ (n=350). (See Section 5.2 for a detailed description of the V114 lots).

A 0.5mL intramuscular dose of the trial vaccine will be administered to healthy infants at approximately 2, 4, 6, and 12 to 15 months of age.

[figure not shown]
The safety and tolerability profile of V114 will be carefully monitored throughout the trial by both the SPONSOR in accordance with standard procedures and by an external Data Monitoring Committee (eDMC). (Details regarding in-house blinding of SPONSOR personnel can be found in Section 5.2.3. ‘Trial Blinding’).

Any trial subject with a serotype-specific anti-pneumococcal immunoglobulin G (IgG) value, as measured by pneumococcal electrochemiluminescence (Pn ECL) assay below 0.35 µg/mL for serotype 19A (individually) or below 0.35 µg/mL for 4 or more of the other serotypes in common with Prevnar 13™ at 1 month post-dose 3 (PD3) will be discontinued from the study and offered an additional dose of licensed pneumococcal conjugate vaccine outside of this protocol. See Section 5.6 (Rescue Medications & Supportive Care) for additional details of the rescue plan.

Specific procedures to be performed during the trial, as well as their prescribed times and associated visit windows, are outlined in the Trial Flow Chart - Section 6.0. Details of each procedure are provided in Section 7.0 – Trial Procedures.

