The vaccines should be administered at a 90° angle in the anterolateral thigh muscle using the provided syringes with the following needle length and gauge specifications¹ : 1 inch needle, 22 to 25 gauge for infants (2-6 months) and 1 to 1¼ inch needle, 22 to 25 gauge for toddlers (12 to 15 months). (See CDC Pink Book, Appendix D for additional details).

To ensure that parents do not become confused regarding the location of the study vaccine injection-site, Doses 1, 2, and 3 of the study vaccine are to be administered in the same limb (e.g., if the study vaccine is provided in the right thigh for dose 1, subsequent doses should also be provided in the right thigh). Dose 4 may be administered in the deltoid region instead of the thigh, at the discretion of the investigator². If an abnormality (i.e., rash) is observed at the site where the previous dose of the study vaccine was administered, it is permissible to use the anterolateral muscle of the other limb to administer the following dose of the study vaccine. (See attachment, CDC Pink Book, Appendix D for additional details).

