7.1.1.8.2 Concomitant Vaccinations

No other investigational compound or device may be administered at any time during this study without prior approval by the SPONSOR.

¹ Needles provided in Prevnar 13TM blister packages may also be used.

² Per investigator discretion, dose 4 can be administered in the deltoid muscle instead of the anterolateral thigh muscle; if given in the deltoid muscle, the needle length should be 5/8 to 1 inch (a 5/8 inch needle may be used only if the skin is stretched tight, subcutaneous tissue is not bunched, and injection is made at a 90-degree angle).

The study vaccines will be administered at approximately 2, 4, 6, and 12 to 15 months of age. Other pediatric vaccines will be administered concomitantly according to the mandated schedule in the site's country/region. These concomitant non-study vaccinations will be recorded on the appropriate eCRF. Combination MMRV vaccines should not be given in this study; however, MMR and Varicella vaccines are permitted if administered concomitantly in 2 separate limbs.

Concomitant vaccines (oral or injectable) should be administered on the same day as study vaccine. Concomitant oral vaccines may be administered prior to the study vaccine and other injectable concomitant vaccines. Precautions must be taken to prevent choking during the administration of oral vaccines. Concomitant injectable vaccines should be administered after the study vaccine. To avoid any confounding results, non-study injectable vaccines should not be administered in the same limb as study vaccine. Documentation of which limb was used for the administration of study vaccine should be recorded on the appropriate eCRF. As we are requesting the reporting of injection-site adverse experiences from the study vaccine (and not from the concomitant vaccines), this information should also be recorded on the VRC to inform the parent/legal guardian of the appropriate limb to monitor for adverse experiences ONLY related to the study vaccine.

During the influenza season, it is anticipated that trial subjects 6 months of age and older may be given an influenza vaccine. Influenza vaccine should be administered either 14 days prior to or 30 days after the administration of the trial vaccine.

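### Table 1 footnote 1 sends every dose to the deltoid, while Section 7.1.1.8.1 requires the anterolateral thigh and allows the deltoid only at dose 4; the footnote should be corrected

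*Combined protocol and SAP*

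**What the plan says.** Table 1 in Section 5.2 lists V114 Lot 1, V114 Lot 2 and Prevnar 13. Each row covers four doses, at about 2, 4, 6 and 12 to 15 months of age. Footnote 1 is attached to the route of administration in all three rows. It states that each "trial vaccine is to be injected into the deltoid muscle of the upper arm", with no exception by age or dose.

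Section 7.1.1.8.1 gives the administration procedure. It places the vaccines "in the anterolateral thigh muscle using the provided syringes with the following needle length" and gauge it then lists by age group. It keeps doses 1, 2 and 3 in one limb, with the example that "if the study vaccine is provided in the right thigh for dose 1, subsequent doses should also be provided in the right thigh". For the last dose it adds: "Dose 4 may be administered in the deltoid region instead of the thigh", at the investigator's discretion. If the earlier site shows an abnormality, "it is permissible to use the anterolateral muscle of the other limb to administer the following dose of the study vaccine". Footnote 2 to that section repeats that "dose 4 can be administered in the deltoid muscle instead of the anterolateral thigh muscle" and gives a needle length for that case.

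**The concern.** Both texts instruct site staff where to inject infants who may be as young as 42 days at dose 1 (Section 5.1.2). They name different muscles for the primary series, and no reading satisfies both. Staff who work from the vaccine table and staff who work from the procedures section would inject doses 1 to 3 at different sites, each with protocol text in support.

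At stake is uniform conduct of the vaccination. A site that follows Table 1 for doses 1 to 3 departs from Section 7.1.1.8.1, and the protocol gives it no deltoid needle length for those doses. The only deltoid-specific length is for dose 4.

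**Working it through.** No arithmetic beyond counting applies, and the plan states no figure to reproduce. The check sets the two rules side by side and then looks for anything that reconciles them.

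**Dose by dose (same in all three arms)**

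| Dose | Table 1, footnote 1 | Section 7.1.1.8.1 and its footnote 2 | Result |
|---|---|---|---|
| 1 | Deltoid | Anterolateral thigh | Direct conflict |
| 2 | Deltoid | Anterolateral thigh, same limb as dose 1 | Direct conflict |
| 3 | Deltoid | Anterolateral thigh, same limb as dose 1 | Direct conflict |
| 4 | Deltoid, mandatory | Thigh by default; deltoid at the investigator's discretion | Partial conflict |

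Direct conflict: 3 of 4 doses. Partial conflict: 1 of 4.

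**Every mention in the current text**

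- The word deltoid appears 4 times: once in Table 1 footnote 1 (all doses), once in the body of Section 7.1.1.8.1 and twice in its footnote 2. The last three are limited to dose 4.
- The word thigh appears 5 times: four in the body of Section 7.1.1.8.1 and once in its footnote 2.
- Neither word appears anywhere else.

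**Does anything reconcile them?**

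- Sections 2.1 and 5.2.2 say only that the injection is intramuscular. The flow chart notes say only that other injectables go in a separate limb.
- The Summary of Changes lists no change to Table 1 or to injection site, so neither text is marked as replacing the other.
- No clause says which section prevails.

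**Which text is wrong?**

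- Section 2.1 says "Details of each procedure are provided in Section 7.0", and the openings of Sections 7.1 and 7.1.5 also treat Section 7 as the place for procedural detail.
- Five statements in Section 7.1.1.8.1 point to the thigh: the main instruction, the same-limb rule with its right-thigh example, the dose 4 alternative, the fallback to the opposite anterolateral muscle, and footnote 2.
- The 1-inch, 22 to 25 gauge needle for ages 2 to 6 months is specified within the thigh instruction. The deltoid needle of 5/8 to 1 inch is specified for dose 4 only.
- A dose 4 option to use the deltoid in place of the thigh makes sense only if the thigh is otherwise the rule.

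Footnote 1 is the only text that puts doses 1 to 3 in the deltoid.

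**The case against.** The strongest reply is that the protocol largely resolves this itself. Section 2.1 refers the reader to Section 7. A vaccinator who needs the needle specification must go to Section 7.1.1.8.1, where the muscle is named. The site that reads only Table 1 is hypothetical, and nothing in the documents shows how often it would occur. The conflict is the same in all arms. On this view the point is editorial. This stands in part: a careful reader can identify the error, and no count of misplaced injections can be given. But the footnote is a mandatory instruction in the table that defines the vaccinations, so being able to work out that it is wrong does not make it acceptable.

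A second reply also has force. The protocol's reason, "To ensure that parents do not become confused regarding the location of the study vaccine injection-site", supports keeping doses 1 to 3 in the same limb. It does not by itself support thigh over deltoid. A site using one deltoid throughout would still meet that purpose, and Sections 5.5 and 7.1.1.8.2 require the limb used to be recorded on the eCRF and the report card. That sentence therefore should not be used to show harm from the choice of muscle, and the conclusion here does not depend on it.

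Third, the five thigh statements all come from one section, and footnote 2 restates a sentence in the body. They are not five independent sources. They do show that the section is coherent, and the footnote has no support anywhere.

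**Conclusion.** The concern holds. The protocol gives incompatible injection-site instructions for doses 1, 2 and 3 and partly incompatible ones for dose 4, in all three arms. Both texts are current and complete. It should be fixed.

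That the footnote is the text to correct is an inference, because there is no precedence clause. It is a strong one: it rests on the consistency of Section 7.1.1.8.1, on its needle specifications, and on Section 2.1 pointing to Section 7 for detail. It does not rely on the external administration reference cited in Section 7.1.1.8.1, whose content is not in the documents.

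No specific hazard and no bias in any comparison is claimed. Sample size, alpha, the non-inferiority margin and the primary analysis are unaffected.

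**What to change.** Replace Table 1 footnote 1 with wording such as: *Doses 1-3 are to be injected into the anterolateral thigh muscle; Dose 4 into the anterolateral thigh or, at the investigator's discretion, the deltoid (see Section 7.1.1.8.1).* Send sites a notice of the correction.

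The cost is one footnote in an amendment and one site notice. Data collection and analysis do not change.

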5.2.1 Dose Selection

5.2.1.1 Dose Selection (Preparation)

The rationale for selection of doses to be used in this trial is provided in Section 4.0 – Background & Rationale. There are no specific calculations or evaluations required to be performed in order to administer the proper dose to each subject.

5.2.2 Timing of Dose Administration

Subjects must be afebrile for at least 72 hours prior to vaccination. In this trial, V114-1, V114-2, or Prevnar 13™ will be administered as an 0.5-mL intramuscular injection at Visit 1 (approximately 2 months of age [≥ 42 or ≤ 90 days of age]), Visit 2 (4 months of age to 1 day prior to 5 months of age), Visit 3 (6 months of age to 1 day prior to 7 months of age) and Visit 5 (12 months of age to 1 day prior to 16 months of age). The day of the first trial vaccination is considered Day 1 of the trial for each subject. Sites should confirm date of birth with subject's parent/guardian and ensure that the age of the subject on the date of vaccination falls within the appropriate age range for each vaccination visit. Subjects should be observed for 30 minutes following vaccination.

Other pediatric vaccines will be administered concomitantly on the same day as trial vaccine according to the recommended schedule. Concomitant oral vaccines may be administered prior to the trial vaccine and other injectable concomitant vaccines. Precautions must be taken to prevent choking during the administration of oral vaccines as aspiration of oral vaccines could occur if the baby is crying or is agitated after receiving the injectable vaccine. Concomitant injectable vaccines should be administered on the same day as trial vaccine and after the trial vaccine has been administered. To avoid any confounding results, non-trial injectable vaccines should not be administered in the same limb as trial vaccine.

